In case of occurrence of any Adverse Event or Adverse Device Effect the appropriate form provided by 3M has to be filled in by the investigator. In case of any near incident or any event that could lead or led to any medical hazard for the investigator (user) of the investigational device the Incident/Near Incident form provided by the sponsor has to be filled in by the investigator.

Any adverse reactions to the treatment provided as part of the study will be fully investigated and recorded on the Adverse Event/Adverse Device Effect form (See Appendix), including details of the appropriate clinical action taken. An adverse event is defined as any unintended adverse experience associated with the study materials or study procedures that results in an unplanned medical assessment or treatment or changes the risk to subjects.

Restoration Failures

If a crown or onlay fails during the term of the study, the investigator will provide complete information on the manner of the failure and the proposed resolution to the study contact person at 3M. Failures associated with the bonding agent, cement, crowns and onlays that may be expected in this study include:

- loosening or complete loss of the crown or onlay

- fracture and/or chipping of the crown or onlay
- surface roughening or discoloration of the crown or onlay

Upon a determination that the crown or onlay failure did not result from other identifiable causes, and with 3M's prior approval, the Institution will make arrangements to replace the crown or onlay or carry out appropriate alternative treatment (i.e. replacement with a fixed or removable partial denture) at 3M's expense. 3M will not be responsible for any expenses incurred without its prior approval. If a crown or onlay fails after the term of the study, 3M will not be responsible for any costs incurred in its repair or replacement. 3M will have no responsibility for any other treatment a patient may receive during the term of the study or after the study has ended.

Monitoring

Monitoring visits will take place at the study center. During these visits, questions on the study conduct will be discussed and the study documentation will be reviewed. The study monitor will check whether the Clinical Investigation Plan was followed and whether the investigational device was applied according to the Instructions for use. The monitor will verify if appropriate patient consent is available for each patient and that it was included before enrolment.

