There will be two datasets analyzed at each recall period; (1) one dataset consisting of subjects who were enrolled up to and including that recall period, and (2) one dataset consisting of all subjects with baseline data. In the second dataset (2) primary and secondary outcome variables which are missing will be imputed using the method of last observation carried forward (LOCF), wherein the last observed values for that variable will be carried forward to all remaining timepoints.

The primary analysis for this study will be the percent of intact/surviving restorations from baseline to the end of each recall period. This will be estimated using the Kaplan-Meier method, there will be no direct comparisons within this analysis. The median survival time of a restoration will be presented alongside survival curves.

The secondary analyses for this study will relate to the FDI criteria for esthetic properties including surface luster, surface staining, margin staining, color match and translucency; functional properties including anatomical form, material fracture, retention,

margin adaptation, occlusal contour and wear, and proximal contact and contour; and biological properties including post-operative sensitivity, caries, gingival index, and plaque index (see Appendix for FDI criteria description). The FDI criteria will be assessed at each recall period versus their respective baseline scores for a particular restoration within a particular subject. FDI criteria which are measured in an ordinal-discrete manner will be assessed using the Wilcoxon-signed rank test. Criteria which are measured continuously such as PI and GI will be assessed using the student's t-test, in the event that the PI and GI scores do not appear to be Normally distributed this assessment will shift to be done using the Wilcoxon-signed rank test.

A two-sided alpha of 0.05 will be used for all comparisons. There will be no adjustments made for multiplicity.

All statistical analyses will be performed e.g. using SAS version 9.4 or above (SAS Institute, Cary, NC).

9 Project Time Line

The recruitment of patients and clinical placement of restorations will begin immediately upon approval and funding of the project. It is anticipated to take 9-12 months to recruit and place the restorations required for the study.

Protocol Amendments and Discontinuing the Study

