After approval of the study protocol, any changes to the content of the study documentation must be described in an Amendment Form and be approved by the PI, 3M, and the reviewing IRB prior to implementation. Any decision as to whether to prematurely stop the study will be taken jointly by the PI, 3M, and the IRB. Where early termination of the study occurs, subjects will receive appropriate follow up dental treatment.

10 Equipment

A CEREC system including a CEREC OmniCam and PrimeScan, MCX mill, Programmat oven, and SpeedFire oven is available at the University of Michigan for use during the study. All other instrumentation required for placement and clinical evaluation of the restorations is available through the Research Clinic of the Department of Cariology, Restorative Sciences, and

Endodontics at the University of Michigan School of Dentistry. Additional measurement instrumentation to include measuring microscopes, scanning electron microscope, computer analysis, and intraoral imaging equipment is available within the School of Dentistry.

11 Facilities

The Graduate General Dentistry Clinic maintains a two chair Clinical Research Unit for clinical research within the department. A full time Clinical Research Coordinator is dedicated to the Clinical Research Unit as well. She will coordinate and schedule all patient appointments, maintain recall schedules, and collate data collected. A Certified Dental Assistant will also provide clinical support as well. Additional dental materials and instruments as well as personnel support will be provided by the Graduate General Dentistry Clinic as needed.

12 Additional Sponsorships:

No other sponsorships are presently available or will be applied to this project.

In the event that study restorations should fail and require replacement, patients may elect to have a laboratory-fabricated restoration placed instead of another test restoration. [REDACTED]

[REDACTED]

[REDACTED]

[REDACTED]

13 References

[figure not shown]
[figure not shown]
[figure not shown]
[figure not shown]

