1. Clinically excellent / very good	5a.1 No fractures / cracks	5b.1 Restoration in place	6.1 Harmonious outline, margins not detectable
2. Clinically good	5a.2 Small hairline crack.	n.a.	6.2 margins detectable: Slight ditching, slight step/flashes, minor irregularities.
3. Clinically sufficient / satisfactory (minor shortcomings, no unacceptable effects but not adjustable w/o damage)	5a.3 Two or more or larger hairline cracks and/or material chip fracture not affecting the marginal integrity or approximal contact.	n.a.	6.3 moderate detectability: Major irregularities, ditching or flash, steps or minor crevice formation
4. Clinically unsatisfactory / (but repairable)	5a.4.1 Material chip fractures which damage marginal quality or approximal contacts	n.a.	6.4.1 major crevice formation 6.4.2 Larger irregularities or steps (repair necessary)
5. Clinically poor (replacement necessary)	5a.5multiple fractures	5b.5 Complete Loss of restoration	6.5 Generalized major gaps/crevice formation or irregularities.

B. Functional properties	7. Occlusal contour and wear	8. Approximal anatomical form a. contact point b. contour
1. Clinically excellent / very good	7.1 No evidence of occlusal wear, wear equivalent to enamel	8a.1 Normal contact point (floss or 25 µm metal blade can pass) 8b.1 Normal contour.
2. Clinically good	7.2 Evidence of local facet formation < 2.0 mm in diameter, no change in occlusal anatomy, wear only slightly different from that to enamel	8a.2. Contact slightly too strong but no disadvantage (floss or 25 µm metal blade can only pass with pressure). 8b.2 Slightly deficient contour.
3. Clinically sufficient / satisfactory (minor shortcomings, no unacceptable effects but not adjustable w/o damage)	7.3 Evidence of local facet formation > 2.0 mm in diameter, slight change in occlusal anatomy, Different wear rate compared to enamel	8a.3. Somewhat weak contact, no indication of damage to tooth, gingiva or periodontal structures; 50 µm metal blade can pass 8b.3 Visible deficient contour
4. Clinically unsatisfactory / (but repairable)	7.4 Evidence of generalized facet formation with evidence of generalized wear altering occlusal anatomic form, Wear considerably exceeds normal enamel wear	8a.4 Too weak and possible damage due to food impaction; 100 µm metal blade can pass 8b.4 Inadequate contour Repair possible.

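### Section 8 carries FDI scores forward without an exception for failed or replaced restorations, so a failure left unscored keeps its pre-failure scores in dataset (2)

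*Combined protocol and SAP*

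**What the plan says.** Section 8 (Statistical Analysis) defines two datasets at each recall. The first is "one dataset consisting of subjects who were enrolled up to and including that recall period"; no imputation is mentioned for it. The second is "one dataset consisting of all subjects with baseline data". In that one, missing primary and secondary outcomes are filled by LOCF, "wherein the last observed values for that variable will be carried forward to all remaining timepoints". Failure and replacement are not treated as exceptions.

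The FDI criteria are the secondary outcomes. Each recall score is compared with the baseline score of the same restoration in the same subject, using the Wilcoxon signed-rank test for ordinal criteria. Section 7.2 schedules evaluations at baseline, six months, and one, two and three years, with four and five years if feasible.

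Section 7.3 (Restoration Failures) lists failures that may be expected, among them "loosening or complete loss of the crown or onlay". The investigator reports how the restoration failed and the proposed resolution to the sponsor; an FDI score at that moment is not requested. Section 12 adds that after a failure "patients may elect to have a laboratory-fabricated restoration placed instead of another test restoration". The FDI form in the Appendix does have a score for loss, "5b.5 Complete Loss of restoration". Score 1 means the restoration is in place, and scores 2 to 4 do not apply to retention.

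Survival is analysed separately, by Kaplan-Meier: "The primary analysis for this study will be the percent of intact/surviving restorations from baseline to the end of each recall period".

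**The concern.** An FDI score that is missing because the restoration has gone differs from one that is missing because the patient skipped a visit. In the first case the outcome itself caused the gap. LOCF as written treats the two alike and fills both with the last score from when the restoration was still there.

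Long-term FDI performance is Specific Aim 3, and loss and fracture are failures the protocol expects. If those failures enter the retention and fracture tables as good scores, the tables understate what they are meant to detect and can disagree with the survival curve in the same report. Leaving the rule open also means that someone decides how to score failures after the data are known.

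**Working it through.** **Inputs.** Section 6.3: 40 crowns and 40 onlays in 60 patients. Section 8: each type analysed separately, two-sided alpha 0.05. Appendix: retention takes only the values 1 and 5. The documents give no failure rate, dropout rate or power calculation, and the sample size rests on a cited guideline, so there is no stated figure to reproduce. I assume k = 1 to 8 losses per 40.

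**Step 1: follow one restoration lost and replaced between two recalls.** At the next recall the original can no longer be examined. Three outcomes are possible under the text:

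- The loss was recorded as retention 5. LOCF carries the 5, and retention is right. Lustre, staining, margin adaptation and wear still carry their last scores for a restoration that is gone.
- The loss was not scored. Retention is missing, and LOCF supplies the last value. That value must be 1, because 2 to 4 do not exist for this criterion.
- The replacement is scored as if it were the original. The scores of a new restoration enter the table and the failure is again not recorded.

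**Step 2: retention with k unscored losses in 40.**

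- True share in place = (40 − k)/40.
- Under LOCF = 40/40.
- If the failed restorations are absent from dataset (1) = (40 − k)/(40 − k) = 100%.
- Mean score with losses set to 5 = (40 − k + 5k)/40. Under LOCF it is 1.00.
- Exact two-sided signed-rank p when all k non-zero differences point the same way = min(1, 2 × 0.5^k). Under LOCF all differences are zero and the test shows no change.

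| k | True in place | LOCF | Dataset (1), failures absent | Mean if scored 5 | p if scored 5 |
|---|---|---|---|---|---|
| 1 | 97.5% | 100% | 39/39 | 1.10 | 1.000 |
| 2 | 95.0% | 100% | 38/38 | 1.20 | 0.500 |
| 4 | 90.0% | 100% | 36/36 | 1.40 | 0.125 |
| 6 | 85.0% | 100% | 34/34 | 1.60 | 0.031 |
| 8 | 80.0% | 100% | 32/32 | 1.80 | 0.008 |

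For k = 4, the loss rate is 4/40 = 10% (exact 95% CI 2.8% to 23.7%), while either dataset could show none.

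**Step 3: a criterion on which survivors also change.** Suppose five surviving restorations worsen by one grade and one further restoration fails on that same criterion. If the failure is scored 5, there are six differences in one direction, and p = 2 × 0.5^6 = 0.031. If LOCF carries its baseline score, there are five, and p = 2 × 0.5^5 = 0.0625. The result at the 0.05 level depends on how that one failure is handled.

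These figures treat restorations as independent, although some patients contribute two.

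**The case against.** The best reply is that the documents do not say failures go unscored. Section 7.2 has two evaluators examine all study restorations and record a consensus on every criterion. The form has a 5 for complete loss and a 5 for multiple fractures, and LOCF acts only on missing values. If the 5 is recorded, LOCF carries it and retention is not biased. Chipping, roughening and discoloration can leave a restoration that is still gradable at the next recall. All of this stands, and it makes the retention effect conditional. It does not answer the failure that is replaced before the next recall, nor the other criteria once the original has gone.

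A second reply concerns dataset (1). It is defined by enrolled subjects, no text withdraws a patient for a failure, and if all 60 patients receive the 80 restorations at no more than two each, 80 − 60 = 20 patients have two. Half of the restorations (40 of 80) then belong to someone with a second study tooth to follow. This also stands, so omission from dataset (1) is possible rather than certain. A patient who stays may still have no score for the original restoration.

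Third, failures are reported in full to the sponsor and the primary analysis can show them. The effect on the retention test is also small: with no other change, at least six losses in 40 are needed for p < 0.05. Both points stand, and they limit the severity. Finally, the text after the replacement sentence in Section 12 is redacted, so its silence on later scoring is weak evidence. The missing exception in Section 8 does not depend on it.

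A reader might infer that every FDI result is biased in favour of the restorations. The documents do not support that. Dataset (1) has no stated imputation, the direction for the gingival and plaque indices cannot be determined, and a lost restoration has no true colour match or lustre against which a carried score could be called too good.

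**Conclusion.** The point holds as a conditional defect in a secondary analysis. The LOCF rule has no exception for failure or replacement, and no failure score is required between recalls. An unscored failure would keep favourable scores in dataset (2). Even a scored one would leave carried-forward values on the other restoration-related criteria. Dataset (1) may omit the same failures.

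The retention overstatement runs from 2.5 to 20 percentage points for 1 to 8 losses in 40 (100% against 97.5% to 80.0%). It is zero if every loss is recorded as 5. The failure counts are assumptions, as is the premise that the failures go unscored. It would be wrong to conclude that failures disappear from the trial's results, since Kaplan-Meier can show those recorded as events. Severity: should-fix, with moderate confidence.

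**What to change.** Add to Section 8, before any recall data are analysed:

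- LOCF is not applied to a restoration after it has failed. Say what counts as failure for this rule, for example loss or replacement, so that a chipped or discoloured restoration still in place continues to be graded as examined.
- From the failure date, the criterion that failed is set to 5 at all later recalls. The restoration stays in the denominator in both datasets, including when the patient has left the study.
- Criteria that can no longer be scored are tabulated as not assessable due to failure, with counts, and are not imputed.
- Scores from a replacement are not used for the original restoration.

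The cost is a few sentences, a small programming rule, and a step that codes the failing criterion from the failure report. The manner of each failure is already reported, so no new data are needed. The FDI tables will look slightly less favourable if failures occur.

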7.2 Clinical Evaluation

Two independent evaluators will examine all restorations in the study. Clinical evaluations will be made at baseline, six months, one year, two years and three years. If feasible, subjects will return for additional follow-up visits at four and five years. Evaluation criteria are based on FDI criteria (Hickel et al., 2007 and 2010) for esthetic properties include surface luster, surface staining, margin staining, color match and translucency; functional properties include anatomical form, material fracture, retention, margin adaptation, occlusal contour and wear, and proximal contact and contour; and biological properties include post-operative sensitivity, caries, gingival index, and plaque index (see Appendix for FDI criteria description). Disagreements in evaluations will be discussed between the evaluators and a consensus judgment will be reached and recorded for every criteria.

Intraoral digital color pictures at a 1:1.5 magnification will be taken to document pre-operative, cavity preparation, and post-operative conditions. Facial and occlusal views of the tooth will be documented for both the pre-operative and post-operative conditions.

A post-cementation quadrant digital scan will be made of each test restoration using the OmniCam. Digital files will be recorded at the baseline, 6 months, 1 year, 2 year and 3 year. Optionally also at 4- and 5-year recall visits. Bite-wing radiographs and periapical radiographs of each test tooth will be available preoperatively and at the three-year recall for routine, standard of care monitoring of the restorations.

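### Last observation carried forward in dataset 2 is not limited to the required visits, so year-4 and year-5 FDI results can contain earlier grades and understate deterioration in criteria that worsen with time

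*Combined protocol and SAP*

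**What the plan says.** Section 8 (Statistical Analysis) sets up two datasets at each recall. Dataset 1 is "one dataset consisting of subjects who were enrolled up to and including that recall period", and no imputation is described for it. Dataset 2 is "one dataset consisting of all subjects with baseline data". In dataset 2, missing primary and secondary outcomes are filled by LOCF, so that "the last observed values for that variable will be carried forward to all remaining timepoints". The FDI criteria are the secondary outcomes, and "The FDI criteria will be assessed at each recall period versus their respective baseline scores", by the Wilcoxon signed-rank test for ordinal criteria.

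Section 7.2 (Clinical Evaluation) fixes the required schedule: "Clinical evaluations will be made at baseline, six months, one year, two years and three years". It then adds: "If feasible, subjects will return for additional follow-up visits at four and five years". For the digital scans it uses the words "Optionally also at 4- and 5-year recall visits", so the plan itself treats years 4 and 5 as recalls. Aim 3 in section 5 covers up to five years of service with a minimum of three.

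No sentence ends the imputation at year 3, restricts dataset 2 at years 4 and 5 to subjects who were recalled, or separates a visit that was never arranged from one that was missed. No expected attendance is given for any visit.

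**The concern.** Because the last two visits are optional, absence there is partly built into the design. Read together, sections 7.2 and 8 give each absent restoration an earlier grade and test that grade as a year-4 or year-5 observation. The point concerns restorations that are intact but were not examined; how failed restorations are graded is a separate matter.

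Carrying a grade forward assumes no change over the interval being reported. Staining, marginal adaptation and wear are scored so that deterioration raises the grade, and they tend to accumulate. For these criteria the error runs in the product's favour and grows as attendance falls. The denominator would still show every subject with baseline data, so a reader of the dataset 2 table could not see how many restorations had been examined that year.

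**Working it through.** The plan gives no attendance rate, expected grade or power figure, so there is no stated number to reproduce. From the documents come the 40 crowns and 40 onlays (section 6.3), analysed separately, and the visit schedule (section 7.2). All rates below are assumptions.

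**Step 1: where year-5 values in dataset 2 come from.** Assume that a patient who misses a visit does not return later. Let a3 be the share graded at year 3, r4 the share of those seen at year 4, and r5 the share of those seen at year 5. Then:

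- observed at year 5 = a3 × r4 × r5
- carried from year 4 = a3 × r4 × (1 − r5)
- carried from year 3 = a3 × (1 − r4)
- carried from an earlier visit = 1 − a3

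With a3 = 0.9, per 40 restorations of one type:

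| r4, r5 | Observed | From year 4 | From year 3 | From earlier |
|---|---|---|---|---|
| 0, 0 (visits not held) | 0 | 0 | 36.0 (90%) | 4.0 |
| 0.25, 0.80 | 7.2 | 1.8 | 27.0 (67.5%) | 4.0 |
| 0.50, 0.80 | 14.4 | 3.6 | 18.0 (45%) | 4.0 |
| 0.80, 0.90 | 25.9 | 2.9 | 7.2 (18%) | 4.0 |
| 0.95, 0.95 | 32.5 | 1.7 | 1.8 (4.5%) | 4.0 |

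With a3 = 1.0 and no later visits, all 40 values are year-3 grades. The year-3 share therefore runs from about 5% to 100%. It exceeds half only when a3 × (1 − r4) > 0.5, that is r4 < 1 − 0.5/a3: below 50% for a3 = 1.0, 44% for a3 = 0.9 and 37.5% for a3 = 0.8.

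**Step 2: effect on a criterion that worsens.** Suppose 30% of restorations have margin staining of grade 2 or worse at year 3 and 50% at year 5. Suppose also that attendance is unrelated to grade and that every year-5 absentee was last seen at year 3. With a share a attending year 5, dataset 2 reports a × 50% + (1 − a) × 30%:

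- a = 0.75: 37.5 + 7.5 = 45%
- a = 0.50: 25 + 15 = 40%
- a = 0.25: 12.5 + 22.5 = 35%

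The shortfall is (1 − a) × 20 points: 5, 10 or 15. The baseline share cancels, so the change since baseline, which is what the plan tests, is understated by the same amount.

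**Step 3: when some absentees were seen at year 4.** Take a = 0.50, half of the absentees seen at year 4, and 40% affected then. Dataset 2 reports 0.50 × 50 + 0.25 × 40 + 0.25 × 30 = 25 + 10 + 7.5 = 42.5%. The shortfall is 7.5 points rather than 10.

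**The case against.** A reader might infer that the five-year FDI results will mostly be three-year grades, or that dataset 2 will show a flat course after year 3. The documents support neither.

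- A majority of year-3 grades needs fewer than about 38% to 50% of those graded at year 3 to be seen again (for 80% to 100% graded then). The plan states no such rate. Sections 6.1 and 6.2 and the enrolment form point the other way: people not available for five years are excluded, and patients are told that long-term availability is needed. Section 11 adds a full-time coordinator who maintains recalls. These provisions make attendance more likely, but section 7.2 still leaves the visits to feasibility.
- A flat course needs no attendance after year 3. The illustration shows weakened rises of 15, 10 or 5 points instead of 20. If the visits are not held at all, section 8 does not say whether a year-5 analysis would be produced.

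Three further objections carry weight. First, dataset 1 is analysed alongside, and a divergence between the two would be visible. That mitigates the problem without curing it: dataset 1 is defined by enrolment rather than examination, and the plan does not say which dataset governs interpretation. Second, the direction of bias is not general, since sensitivity can resolve and plaque and gingival scores can move either way. Third, no contrast of year 3 with year 5 is planned; the tests are against baseline, and a carried year-3 grade still shows change up to year 3. The shortfall in Step 2 applies to that comparison.

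**Conclusion.** The concern holds as a bias in one of two datasets, for secondary outcomes, at two optional visits. As written, the rule enters grades from year 4, year 3 or earlier as later observations, in a proportion set by attendance that the plan does not state. For staining, marginal adaptation and wear this understates deterioration since baseline. On the assumed 30% and 50%, the understatement is 5, 10 or 15 points at 75%, 50% or 25% attendance, and less if some absentees were seen at year 4. Those figures rest on attendance being unrelated to grade. They illustrate the mechanism and do not forecast this trial's results. Because the rule is stated and its effect on these criteria is foreseeable, it should be changed before the analysis.

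**What to change.** Amend section 8 so that dataset 2 and its LOCF stop at the required recalls, through year 3. Report FDI results at years 4 and 5 on restorations actually examined. Beside them give the number examined over the number still in service, and the year-3 grades of attenders and non-attenders, so that a reader can judge whether those who returned differ from those who did not.

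This takes a short amendment to the analysis text and no new data. The downside is smaller denominators at years 4 and 5. The change does not address visits missed before year 3, where carrying a grade forward makes the same assumption of no change.
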